8.2 Subject Revocation of Authorization to Use & Disclose Personal Health Information

In order to implement a valid revocation of authorization, the subject must make the request in writing to Eastern Regional Medical Center, Inc. [name]. The revocation cannot stop the use or disclosure of information that has been collected prior to the revocation, is needed to ensure complete and accurate study results, or is required by law or government regulation (e.g. reporting adverse events, etc.). Revocation of an authorization may not be used to withhold normal medical care from the subject, but will make the subject ineligible to receive study care.

8.3 Confidentiality of Data

The Principal Investigator will oversee the conduct of the study and all data will be kept confidential. Confidentiality will be maintained by using patient identification numbers instead of names. Consent forms, data collection sheets and records, linking a subject's name with their ID number will be maintained in a locked cabinet or locked office. Information to be stored on the computer will be identified by subject ID and will be password protected. Data disclosed outside the study team will be de-identified or will only include general group demographic information. Protected Health Information and/or identifiable study data will not be shared with anyone outside the study team or Health System, with the exception of the study sponsor, and federal regulators/ institutional officials for the purposes of auditing.

Page 18 of 43 Status: Release Version: 1

Issue Date: 10/5/2016 9:39:53 AM

Subject medical information obtained by this study is confidential, and disclosure to third parties other than those noted below is prohibited.

Upon the subject's permission, medical information may be given to his or her personal physician or other appropriate medical personnel responsible for his or her welfare.

Data generated by this study must be available for inspection upon request by representatives of the U.S. FDA, national and local health authorities, the device manufacturer, and the IRB.

9. Screening and Enrollment

A representative from the site will complete the following screening and enrollment activities:

- Obtain Informed Consent
 - Explain the study to the subject, answer questions, and obtain written informed consent
- Review the Inclusion/Exclusion Criteria
- Perform assessments required by the Inclusion/Exclusion criteria
 - Collect urine sample and perform urine pregnancy test for female subjects who are of childbearing age. If the subject is post-menopausal, no pregnancy test is required.

If a subject does not meet all the Inclusion/Exclusion criteria, the subject will be excluded from the study.

If a subject meets all the Inclusion/Exclusion criteria, the Investigator, study nurse, or research staff (when appropriate) will complete the following remaining screening activities:

- Record subject demographics.
- Obtain and record history.
- Obtain and record information describing current medications and treatment
 - Oral or systemic medications prescribed by the subject's physician are allowed and will be noted on the appropriate CRF.
 - Use of moisture barrier, creams, ointments, pastes, or other topical medications in combination with the product are **not** allowed.

10. Study Assessments

10.1 Study Product Application and Assessment-Initial and Follow-up Visits

Day 0 (Enrollment) - Initial product application and skin assessments Week 1 (Day 3 ± 24 hours) - product application and assessment

Page 19 of 43 Status: Release

Version: 1

Issue Date: 10/5/2016 9:39:53 AM

Week 1 (Day 6 ± 24 hours) -product application and assessment

Week 2 (Day 9 ± 24 hours) -product application and assessment

Week 2 (Day 12 ± 24 hours) -product application and assessment

Day 14 (End of Study) – skin assessments will be completed at the final visit.

Unscheduled visits - product application and assessments will be completed if more product applications are needed due to leakage, skin irritation or standard of care.

Perform skin cleansing:

- Use plain tap water or normal saline which is standard practice
- Avoid rigorous scrubbing to minimize friction damage.
- Record pain score assessment using Faces Pain Scale Visual Analog

Conduct skin assessment for each site (the 4 inch x 4 inch area around the ostomy, drain, or fistula will be referred to as the "site" in this study)

- O Complete a skin assessment:
 - Periwound skin condition
 - Percentage of site: normal skin, intact pink and/or red skin, epidermal loss
 - Presence of lesions
 - Signs of fungal infection

• Study Product Application

- Following cleansing, the 3M[™] Cavilon[™] Advanced Skin Protectant will be applied
- Apply 3M[™] Cavilon[™] Advanced Skin Protectant to the area surrounding the ostomy, drain or fistula (approximately 4 inches x 4 inches)
- Use a new applicator of 3M[™] Cavilon[™] Advanced Skin Protectant for each type of site (ostomy, drain or fistula)
- Record the number of applicators of the 3M[™] Cavilon[™] Advanced Skin Protectant used for each site (ostomy, drain or fistula)
- Record pain score assessment using Faces Pain Scale Visual Analog during and after cleansing and application of the product (primary site only)
- If there should be a need for product removal, use adhesive remover and gently wipe the area.

• Take photographs (one photograph for each site after cleansing)

- Position the subject appropriately to take photos; one photo for each site the product is applied.
- Take a photograph including the paper ruler in the photo (label paper ruler with patient information-patient number, date of visit, and site location)
- Download photographs into the EDC system

Medications

Review and record changes to current medications.

Adverse Events

 Assess and record adverse events. Immediately report any Serious Adverse Event. (Refer to Adverse Event CRF instructions).

Additional Observation

Page 20 of 43 Status: Release

Version: 1

Issue Date: 10/5/2016 9:39:53 AM

Observe area for any signs of fungal infections

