10.3 Schedule of Events

Assessment	Screening / Enrollment Day 0	Week 1 Day 3 (± 24 hours)	Week 1 Day 6 (± 24 hours)	Week 2 Day 9 (± 24 hours)	Week 2 Day 12 (± 24 hours)	Unscheduled Visit (any time there is an issue with the site)	End of Study or Day 14
Informed Consent	Х					,	
Inclusion/Exclusion	Х						
Urine Pregnancy Test	х						
Demographics	Х						
History & Current Product Use	х						
Medications	Х	Х	Х	Х	Х	Х	Х
	Х						Х
Skin Cleansing	Х	Х	Х	Х	Х	Х	Х
Skin Assessment / scoring	х	X	Х	Х	Х	Х	Х
Photographs	Х	Х	Х	Х	Х	Х	Х
Product Application	Х	Х	Х	Х	Х	Х	
Adverse Events	Х	Х	Х	Х	Х	Х	Х
							Х
Protocol Deviation	Х	Х	Х	Х	Х	Х	Х

Page 22 of 43 Status: Release

Version: 1

Issue Date: 10/5/2016 9:39:53 AM

11. Subject Discontinuation

The Investigator may discontinue individual subjects from the study at any time. Subjects may voluntarily withdraw from the study at any time. The Investigator or study nurse will indicate on the appropriate CRF reason for, and date of, subject discontinuation.

Possible reasons for discontinuation are listed below:

- A subject develops a bacterial or fungal infection in the area included in the study or any
 other condition requiring the use of a topical treatment. Data collected up to the time where
 the subject required topical treatment will be analyzed.
- A subject develops any condition which, in the opinion of the Investigator, requires
 discontinuation from the study. If this condition is a suspected localized allergic reaction to
 the product, then appropriate testing confirmation should be performed and results/reports
 should be submitted to 3M. In addition, the event should be entered on the Adverse Event
 CRF.

The expectation is that subjects will be enrolled in this study for a period up to14 days. A subject who discontinues prior to their first assessment following product application, will be replaced with another qualified subject.

12. Subject Compliance

Subject compliance is not an issue in this study as subjects will not be applying the product themselves. CRFs will be used to monitor the number of cleansing episodes, and number of product application(s), performed by skilled care givers.

13. Study Supplies

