15.1 Study Risks

The potential risks involved in this clinical study are considered to be consistent with those associated with similar skin protectant products used for the management and prevention of skin around ostomies/drains and fistulas. These risks include but are not limited to skin irritation.

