15.3 Anticipated Benefits

The potential benefit of this product is that it is able to attach to moist or wet, damaged skin forming an adherent, protective coating that creates an environment for healing. It will provide better skin protection of damaged skin against irritants such as gastric fluid or wound drainage. It will also allow adherence of a pouch.

Risk to Benefit Rationale

The study product is classified as non-significant risk. Based on data collected in previous studies, the risk-to-benefit ratio is within reason for foreseeable risks. However, appropriate observation and follow-up of subjects, will still be required as outlined in the protocol.

16. Safety Reporting

Adverse events will be collected for subjects beginning at Day 1 through the final study visit, or until the subject is discharged from the facility. An adverse event is any symptom, sign, illness, or experience, which develops or worsens during the course of the study, which may or may not be considered product related. The principal measures of safety will be the incidence of adverse events reported during the study.

An anticipated adverse event in this study is a skin reaction to the product itself. Worsening of the skin condition is expected in this subject population and would therefore not constitute an adverse event (related to the product being tested).

Page 26 of 43 Status: Release Version: 1

Issue Date: 10/5/2016 9:39:53 AM

The Adverse Event CRF will be used to capture any safety-related concerns.

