16.1 Adverse Events

The Investigator is responsible for identifying and reporting adverse events experienced by each subject throughout the study. An adverse event can occur at any time during the conduct of the study, in any phase of the study, or after the study is completed. An adverse event can be identified by the Investigator or reported by the subject.

Note: The Federal Privacy Rule (HIPAA) specifically permits the use and disclosure of protected health information "without written authorization of the individual" when used for public health activities such as reporting adverse events, tracking FDA-related products, enabling recalls, repairs, replacements, lookbacks, or conducting post-market surveillance [45 CFR 164.512]. This use and disclosure is subject to the *minimum necessary* standard, i.e. "the minimum necessary to accomplish the intended use, disclosure, or request" [45 CFR 164.502(b)(1)].

An adverse event is considered to be **serious** if it is:

- Life threatening of results in death
- Causes in-patient hospitalization
- Unduly prolongs hospitalization
- Persistently or significantly disabling
- A congenital anomaly
- Requires intervention to prevent outcomes above

Severity:

All adverse events will be classified as one of the following severities:

Mild: Subject is aware of signs or symptoms but they are easily tolerated.

Moderate: Signs or symptoms are sufficient to restrict but not prevent subject's daily activity.

Severe: Subject unable to perform daily activity.

Definitions:

- Adverse event (AE) means any undesirable clinical occurrence in a subject whether or not it
 is considered to be device related.
- Device-related adverse event (i.e. adverse device effect) is an AE considered by the Investigator to have a reasonable likelihood of being associated with the device.
- Serious adverse device effect (SADE) is a device effect that has a serious adverse effect on health or safety causing hospitalization or prolonged hospitalization, or is life threatening or causes death.

Page 27 of 43 Status: Release Version: 1

Issue Date: 10/5/2016 9:39:53 AM

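### Skin irritation is both a trigger for more product and the named risk, while worsening skin is excluded from (product-related) adverse events with no rule to separate it from a product reaction

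*Combined protocol and SAP*

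**What the plan says.** - **Section 10.1** has product application and assessments at unscheduled visits "if more product applications are needed due to leakage, skin irritation or standard of care". It does not separate irritation caused by leaked fluid from irritation caused by the product.
- **Section 15.1** says of the study risks: "These risks include but are not limited to skin irritation". No other risk is named there.
- **Section 16**, opening text, defines an AE as something "which develops or worsens during the course of the study, which may or may not be considered product related". It then states: "An anticipated adverse event in this study is a skin reaction to the product itself". The next sentence reads "Worsening of the skin condition is expected in this subject population and would therefore not constitute an adverse event (related to the product being tested", and the parenthesis closes the sentence.
- **Section 16.1** gives a second definition: an AE "means any undesirable clinical occurrence in a subject whether or not it" is thought to be due to the device.
- **Section 16.2** has relationship to the product documented for each event on a four-level scale.
- **Sections 10.1 and 10.3** call for AE assessment at each visit. The schedule marks AEs, skin assessment, photographs and product application for the unscheduled visit.
- **Section 6.7** bases safety on the number and percent of subjects with an AE, with summaries by relation to product and by severity. Section 16 makes AE incidence the principal safety measure, and section 5.1 puts safety in the primary objective.

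**The concern.** Inclusion criterion 2 (section 7.1) requires red, broken-down skin at the site. A reaction to the product and a deterioration of the enrolling damage may therefore look alike at a visit. The protocol makes the first an AE and removes the second from the AEs, or from the related ones, without saying how to tell them apart. Irritation is also a stated reason to apply more product, and no judgement of cause is required before that happens.

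A true reaction could thus be read as worsening, be followed by another application, and be absent from the AE table or from its related column. The study has a single arm and no comparator to reveal under-counting. With at most 30 subjects, a few misclassified cases would change what the safety table shows.

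**Working it through.** The documents state no AE rate, power or error level for safety, so there is no figure to reproduce. The check is mainly textual.

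**Step 1: the exclusion against the definitions.** The section 16 definition covers anything that gets worse during the study, whatever the cause. The section 16.1 definition covers any undesirable occurrence, whatever the cause. Worsening skin meets both, yet a later sentence in section 16 removes it. The reason given is that worsening is expected, but neither definition makes exceptions for expected events. The same paragraph calls a product skin reaction both anticipated and an AE.

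**Step 2: the two readings of the parenthesis.**
- *Reading A:* worsening is not an AE. Cases leave the overall incidence and every breakdown of it.
- *Reading B:* worsening is an AE but not a product-related one. Overall incidence is intact, but relatedness is fixed in advance instead of being judged on the section 16.2 scale.

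Under both readings, a product reaction classed as worsening is missing from the related-AE summary in section 6.7.

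**Step 3: whether the safeguards close the gap.** AE assessment at every visit and the relatedness scale apply once someone accepts that the finding is an AE, which is the decision that section 16 leaves unclear. Skin assessments and photographs would leave a trace. However, the safety analyses in sections 6.7 and 17.1.2 summarise AEs and discontinuations, so that trace would not reach the safety tables.

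**Step 4: illustration of size.** From section 6.3: n = 30 in all, 10 per site type. Assumed, because the documents give neither: p, the true share of subjects with a product skin reaction, and m, the share of those classed as worsening.

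Expected number counted = n × p × (1 − m). Chance of counting at least one = 1 − [1 − p(1 − m)]^n.

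| n | p | Expected, m = 0 | Expected, m = 50% | At least one, m = 0 | At least one, m = 50% |
|---|---|---|---|---|---|
| 30 | 5% | 1.5 | 0.75 | 78.5% | 53.2% |
| 30 | 10% | 3.0 | 1.5 | 95.8% | 78.5% |
| 30 | 20% | 6.0 | 3.0 | 99.9% | 95.8% |
| 10 | 10% | 1.0 | 0.5 | 65.1% | 40.1% |

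For example, 30 × 0.10 × 0.5 = 1.5, and 1 − 0.95^30 = 78.5%. At m = 100% every entry is zero.

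**The case against.** The strongest reply is that the protocol does not call irritation a non-event. A reader might infer that it does, but the excluded item is worsening of the skin, and the sentence before it makes a product reaction an AE. Placing irritation under the exclusion is an inference about how staff may apply the text. This stands, and the point is limited accordingly.

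Three other strong readings also fail:

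- *Re-application replaces AE recording.* It does not. AEs are to be assessed at unscheduled visits, and nothing in section 10.1 lets one stand in for the other.
- *The protocol handles irritation in several conflicting ways.* Section 15.1 only states a risk. The section 11 instruction begins "If this condition is a suspected localized allergic reaction to" the product. It concerns a condition that the investigator judges to require discontinuation, and it sends the event to the AE CRF. That is a safeguard, though it does not cover non-allergic irritation.
- *The safety result is wrong by a known amount.* Suppose 3 of 30 subjects react and none is recorded. The related count is then 0/30 (exact 95% interval 0 to 11.6%) instead of 3/30 (2.1 to 26.5%). The intervals are correct, but both the rate and total misclassification are assumed.

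The CRFs and their instructions are not in the public document and may contain a criterion, so no gap in them is alleged. What remains is the clash between the exclusion and the definitions, and the lack of a dividing rule in the text that can be read.

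**Conclusion.** The concern holds in limited form. The exclusion in section 16 conflicts with the AE definitions in sections 16 and 16.1, and no visible criterion separates expected worsening from the product reaction that section 16 counts as an AE. Because irritation is both the named risk and a reason for more product, this ambiguity falls on the harm that the protocol itself anticipates.

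Overall AE incidence (reading A), or at least the related-AE summary (either reading), may be biased low. The exclusion can only remove events or the related label; it cannot add either. The size is unknown. With an assumed 10% true rate in 30 subjects and half misclassified, 1.5 of 3.0 expected cases would be counted. That figure concerns product skin reactions only. A subject with another recorded AE would still count in the overall percentage.

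**What to change.** 1. Reconcile sections 10.1, 16 and 16.1 so that they agree on how irritation at the site is classified. How it is managed clinically, including whether product is applied again, is for the sponsor and investigator to settle.
2. Remove the blanket exclusion of worsening from section 16, so that the definitions already given apply and relatedness is judged case by case on the section 16.2 scale.
3. Record new or worsened skin irritation at the site on the existing AE CRF, with severity and relatedness, whether or not product is re-applied. This should apply at every post-application visit, scheduled or unscheduled; limiting it to unscheduled visits would leave the same ambiguity at Days 3, 6, 9 and 12.
4. Tabulate these events by relatedness and by site type.

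The cost is a wording change in a few sections, one CRF instruction and one table. More events will be recorded, some of them caused by effluent and not by the product, and the AE table will look less favourable. The breakdown by relatedness lets a reader see how much of the increase is attributed to the product.

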10.2 Final Study Visit

The subject's participation in this study is completed after 14 days of follow-up or last visit. At the final visit the following assessments will be completed:

Medications

Review and record changes to current medications.

Adverse Events

- Assess and record adverse events. Immediately report any Serious Adverse Event. (Refer to Adverse Event CRF instructions).
- Perform skin cleansing and record pain score using the Visual Analog Faces Pain Scale
- Take photographs (one photograph for each site after cleansing)
 - Position the subject appropriately to take photos; one photo for each site the product is applied.
 - Take a photograph including the paper ruler in the photo (label paper ruler with patient information-patient number, date of visit, and site location)
 - Download photographs into the EDC system
- Conduct skin assessment for each site (the 4 inch x 4 inch area around the ostomy, drain, or fistula will be referred to as the "site" in this study)
 - O Complete a skin assessment:
 - Periwound skin condition
 - Presence of lesions
 - Percentage of site: normal skin, intact pink and/or red skin, epidermal loss
 - Signs of fungal infection

Documentation

Complete and check all documentation.

Page 21 of 43 Status: Release Version: 1

Issue Date: 10/5/2016 9:39:53 AM

10.3 Schedule of Events

Assessment	Screening / Enrollment Day 0	Week 1 Day 3 (± 24 hours)	Week 1 Day 6 (± 24 hours)	Week 2 Day 9 (± 24 hours)	Week 2 Day 12 (± 24 hours)	Unscheduled Visit (any time there is an issue with the site)	End of Study or Day 14
Informed Consent	Х					,	
Inclusion/Exclusion	Х						
Urine Pregnancy Test	х						
Demographics	Х						
History & Current Product Use	х						
Medications	Х	Х	Х	Х	Х	Х	Х
	Х						Х
Skin Cleansing	Х	Х	Х	Х	Х	Х	Х
Skin Assessment / scoring	х	X	Х	Х	Х	Х	Х
Photographs	Х	Х	Х	Х	Х	Х	Х
Product Application	Х	Х	Х	Х	Х	Х	
Adverse Events	Х	Х	Х	Х	Х	Х	Х
							Х
Protocol Deviation	Х	Х	Х	Х	Х	Х	Х

Page 22 of 43 Status: Release

Version: 1

Issue Date: 10/5/2016 9:39:53 AM

11. Subject Discontinuation

The Investigator may discontinue individual subjects from the study at any time. Subjects may voluntarily withdraw from the study at any time. The Investigator or study nurse will indicate on the appropriate CRF reason for, and date of, subject discontinuation.

Possible reasons for discontinuation are listed below:

- A subject develops a bacterial or fungal infection in the area included in the study or any
 other condition requiring the use of a topical treatment. Data collected up to the time where
 the subject required topical treatment will be analyzed.
- A subject develops any condition which, in the opinion of the Investigator, requires
 discontinuation from the study. If this condition is a suspected localized allergic reaction to
 the product, then appropriate testing confirmation should be performed and results/reports
 should be submitted to 3M. In addition, the event should be entered on the Adverse Event
 CRF.

The expectation is that subjects will be enrolled in this study for a period up to14 days. A subject who discontinues prior to their first assessment following product application, will be replaced with another qualified subject.

12. Subject Compliance

Subject compliance is not an issue in this study as subjects will not be applying the product themselves. CRFs will be used to monitor the number of cleansing episodes, and number of product application(s), performed by skilled care givers.

13. Study Supplies

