	# of Subjects per site: up to 30 subjects

Page 9 of 43 Status: Release Version: 1

Issue Date: 10/5/2016 9:39:53 AM

Assessments:	Study Assessments:
	Subjects will be screened for the Inclusion/Exclusion criteria
	History, demographics, and medications will be documented at baseline.
	 Subjects will remain in the study for up to 14 days following enrollment, receiving the product. Skin assessments will be performed on product dosing days. Assessments will be done using a clinical skin assessment (described below) and photographs.
	 Subject's response regarding pain scores will be tracked following cleansing and product application.
	Quantity of products used will be tracked.
	Data Sets Analyzed:
	The primary efficacy data set will be the data set that will consist of subjects who have at least one skin assessment post-baseline. Dropouts will be censored at time of dropping out.
	Efficacy Analysis:
	 The primary response will be the percent change in area of epidermal loss between the areas observed at baseline subtracted from the area of epidermal loss at each time point. In addition, the time to re-epithelialization will be estimated using a Kaplan-Meier method. These will be summarized overall as well by each type of site (ostomy, drain, and/or fistula).
Data Analysis Planned:	 Pain scores assessed by the visual analog scale will be compared between baseline and each time point post-application of the barrier film. A paired t-test will be done to assess the significance of the change from baseline. These will be summarized overall as well by each type of damaged skin (ostomy, drain, and fistula).
	•
	 Safety Analysis: Overall incidence of adverse events will be documented. The safety analysis data set will consist of all subjects enrolled in the study who received at least one application of the test material.

Page 10 of 43 Status: Release Version: 1

Issue Date: 10/5/2016 9:39:53 AM

2. Background Information

The skin is the protective layer of the body and provides an important anatomical barrier to pathogens, irritants, water loss and environmental threats. Various conditions can damage the skin and breach integrity of the barrier. This can result in inflammation, disruption of epidermal integrity, pain and can increase the risk of infection.

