6.3 Sample Size

A maximum of 30 subjects (10 subjects each for ostomy, drain and fistula) will be enrolled. A sample size of 30 is usually sufficient to estimate the distribution of a population and provide an estimate of performance for future studies.

Page 15 of 43 Status: Release Version: 1

Issue Date: 10/5/2016 9:39:53 AM

6.4 **Study Duration**

In order to screen, enroll, and complete up to 30 evaluable subjects, an enrollment period of is anticipated. 3M™ Cavilon™ Advanced Skin Protectant is indicated for application every 72 hours. Patient will return or be seen inpatient every 72 hours (±24 hours) for evaluation of product application. Assessment of denuded surface area will be measured at baseline. follow-up visits, and at the end of the study typically at day 14 but may be sooner if wound resolves at an earlier date. As previously noted, each subject may be followed for up to 14 days.

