17.2 Sample Size Justification

This is an observational study with a maximum of 30 subjects enrolled with either an ostomy, drain, or fistula.

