17.4 Procedures for Accounting for Missing, Unused, and Spurious Data

The Kaplan-Meier estimate of time to healing of skin will censor any missing data due to subjects completing the study early. Any other missing data will be documented, and decisions on the use of the data will be documented in the Statistical Analysis Plan.

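### Treated subjects who leave before any post-application skin assessment are replaced and fall outside the primary efficacy set, so the healing and pain estimates may be too favourable; what the figure of 30 counts is also unreconciled

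*Combined protocol and SAP*

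**What the plan says.** **Replacement.** Section 11 (Subject Discontinuation): "A subject who discontinues prior to their first assessment following product application, will be replaced with another qualified subject". No limit is put on the number of replacements.

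**Efficacy set.** The part of the synopsis on data sets gives this definition: "The primary efficacy data set will be the data set that will consist of subjects who have at least one skin assessment post-baseline". The next sentence reads: "Dropouts will be censored at time of dropping out".

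**Missing data.** Section 17.4: "The Kaplan-Meier estimate of time to healing of skin will censor any missing data due to subjects completing the study early". Other missing data are left to decisions to be documented in the SAP.

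**Sample size.** Section 6.3: "A maximum of 30 subjects (10 subjects each for ostomy, drain and fistula) will be enrolled". Section 17.2: "This is an observational study with a maximum of 30 subjects enrolled with either an ostomy, drain, or fistula". Section 6.4, however, sets the timeline needed to "complete up to 30 evaluable subjects".

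**Provisions that limit the problem.** Sections 10.1 and 10.3 provide unscheduled visits with a skin assessment when there is a problem at the site. Section 10.2 includes a skin assessment at the last visit. The synopsis keeps every subject with at least one application in the safety set. Section 6.7 summarizes discontinuations by reason.

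**The concern.** Taken together, the replacement rule and the set definition remove a treated subject with no post-application skin assessment from the efficacy result and put a new subject in that place. Whether a subject is removed can depend on how the product performed. Section 11 lists infection in the study area, a condition needing topical treatment, and a suspected local allergic reaction to the product among the possible reasons for stopping.

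The safety tables may not fill the gap. Section 16 says that worsening of the skin condition is expected and does not count as an adverse event. A parenthesis there may limit this to product-related events. On the wider reading, a subject whose skin worsened and who left unseen would appear only in the discontinuation summary.

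Pain, the second primary endpoint, is affected as well. Section 10.1 records pain during and after the Day 0 application, and section 2 makes comfort on application a study question. A subject who withdraws after the first application could have that score and still fail a set definition that rests on skin assessments.

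The study has one arm, and section 6.3 says its purpose is to estimate performance for future studies. The estimate itself is therefore what is at stake.

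**Working it through.** **Inputs from the documents.** Maximum of 30 subjects, 10 per site type (6.3); first scheduled follow-up at Day 3 ± 24 hours (10.1); follow-up to Day 14; dropouts censored (synopsis). The documents give no expected healing rate, early-leaver rate, alpha, power or SD. Healed counts and leaver counts below are assumptions.

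**1. The plan's own figure.** 3 site types × 10 = 30, which reproduces.

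**2. Crude healed proportion.** With h healed among n analysed and k replaced leavers counted as unhealed, h/n becomes h/(n + k), a drop of (h/n) × k/(n + k).

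| Assumed result | k = 0 | k = 1 | k = 3 | k = 5 |
|---|---|---|---|---|
| 15 healed, n = 30 | 50.0% | 48.4% | 45.5% | 42.9% |
| 20 healed, n = 30 | 66.7% | 64.5% | 60.6% | 57.1% |
| 21 healed, n = 30 | 70.0% | 67.7% | 63.6% | 60.0% |

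For one site type of 10, one leaver moves 5/10 = 50.0% to 5/11 = 45.5%, or 7/10 = 70.0% to 7/11 = 63.6%.

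The effect does not depend on going above 30. If 30 are enrolled in all and 3 leave early, 19/27 = 70.4% becomes 19/30 = 63.3%.

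**3. Kaplan-Meier, the planned healing analysis.** Illustrative data for 30 subjects: 5 heal at Day 6, 6 at Day 9, 5 at Day 12 and 5 at Day 14; 9 are unhealed at Day 14. Add three early leavers in three ways:

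- Excluded: unhealed = 25/30 × 19/25 × 14/19 × 9/14 = 0.300, so 70.0% healed.
- Included but censored at Day 0: they have left before the first healing event, every risk set is the same, and the result is again 70.0%.
- Kept at risk as unhealed to Day 14: unhealed = 28/33 × 22/28 × 17/22 × 12/17 = 12/33 = 0.364, so 63.6% healed.

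Widening the set therefore does nothing by itself; the counting rule decides.

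**4. Percent change in epidermal loss.** Assume a mean of −60% in 30 subjects. With k leavers set to no change, the mean is −60 × 30/(30 + k): −58.1% for k = 1, −54.5% for k = 3, −51.4% for k = 5.

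**5. What 30 counts.** With early-leaver rate d, 30 evaluable subjects require 30/(1 − d) enrolled, rounded up.

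| Assumed d | Enrolled for 30 evaluable | Expected evaluable if 30 is a hard enrolment cap |
|---|---|---|
| 5% | 32 | 28.5 |
| 10% | 34 | 27.0 |
| 15% | 36 | 25.5 |
| 20% | 38 | 24.0 |

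The chance of at least one early leaver among 30 is 1 − (1 − d)^30: 79% at 5% and 96% at 10%. The question is likely to arise in practice even at a low rate.

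**The case against.** The strongest reply is that a subject whose product fails early is usually seen. Leakage or irritation that calls for re-application triggers an unscheduled visit with an assessment, and the last visit includes one too. One such assessment puts the subject in the efficacy set. A reader might infer that the earliest product failures vanish from the result; the documents do not support that. Leakage and intolerable application are not among the reasons for stopping in section 11, and some leavers will go for unrelated reasons. What remains is narrower. For a subject who discontinues, section 11 expressly requires only the reason and date, so some may leave unassessed.

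A reader might also infer that replacement necessarily breaks the cap of 30. It does not: both limits are worded as ceilings, and replacements can be taken within 30. The cap is exceeded only if 30 evaluable subjects are sought and at least one is replaced.

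It is fair to say that a crude healed proportion is not a planned analysis. The Kaplan-Meier check answers this in part: exclusion and Day 0 censoring give the same curve, so censoring has the same effect as exclusion. Making failure imputation the primary analysis would go too far. It would treat unrelated withdrawals as failures and, if applied to early leavers alone, would sit badly with the censoring of later dropouts.

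Finally, section 17.4 defers other missing-data decisions to the SAP. No separate SAP text is in the document, so a sensitivity analysis there cannot be ruled out.

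**Conclusion.** The point holds in limited form. Early leavers without any post-application assessment are replaced and excluded, and nothing in the document counts them as unhealed. The healing and pain estimates are too favourable if those leavers do worse than the subjects analysed; the documents do not establish that they do.

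The size depends on assumed counts. Three replaced subjects move 67% healed to 61%, and in a site type of 10 a single one moves 50% to 45%. These figures count every leaver as unhealed, so they show the unfavourable end. Setting leavers to no change in epidermal loss is not a worst case, because their skin may have worsened.

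The study plans no formal hypothesis test, so the consequence is for the estimate carried into future studies and not for type I error or power. On sample size, the defect is unreconciled wording on enrolled versus evaluable, not a demonstrated breach. This is an inexpensive improvement worth making.

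**What to change.** 1. Keep the planned efficacy set as primary.
2. Add a sensitivity analysis in all subjects with at least one application. Every subject who discontinues without re-epithelialization, early leavers and later dropouts alike, stays at risk as unhealed to Day 14. Early leavers are given no change in epidermal loss.
3. Include any Day 0 post-application pain scores from early leavers in the pain summary.
4. Report the number, site type and reason for all replaced subjects beside the efficacy result.
5. Reconcile sections 6.3, 6.4, 11 and 17.2 by stating whether 30 means enrolled or evaluable and whether replacements count toward it.

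The cost is wording in those sections, the synopsis and the SAP, plus one extra analysis. The downside is a possibly less favourable healing figure to show beside the planned one.
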